#### **Exploratory Efficacy Endpoints:**

Exploratory efficacy endpoints include:

- Likelihood of the need for joint replacement surgery, based on KOOS subscales and SS outcomes, from Baseline through Week 8
- Subject satisfaction with the treatment of the index knee through Week 8 of the trial (7-point Likert Scale where 1=completely dissatisfied and 7=completely satisfied)
- The effect of subject characteristics (including K-L grade, sex, BMI, age, unilateral/bilateral knee OA, bilateral knee OA treatment, and history of contralateral PJR/TJR) on the analgesic efficacy of CNTX-4975-05, using the KOOS subscales at each study visit through Week 8
- Frequency of use of background analgesic medication for pain in the injected knee(s) throughout the study period.
- Assessment of the mean of the individual outcome measures, using the average of both knees for the subjects who received bilateral knee injections

#### Safety endpoints:

- Adverse events
- Vital signs
- Clinical laboratory evaluations (hematology, chemistry, and urinalysis)
- 12-lead ECGs
- Physical examination (including the presence or absence of an effusion in the index knee, periarticular pain/tenderness)
- Concomitant medications and therapies
- Degree of procedure pain (not recorded as AEs)
- Local physical findings after injection of the index knee
- Injection site assessment of erythema and edema
- Sensory testing

## STATISTICAL METHODS

The primary analysis will compare each experimental treatment regimen to the Breg Cooling Control Group using an equally-weighted, combined score calculated from the following 3 measures: 1) pain 30 minutes after CNTX-4975-05 injection (using the 0-4 scale of none, mild, moderate, moderately severe, and severe), 2) SS with the treatment regimen; and 3) IS with the treatment regimen, all assessed on the index knee. Ratios of the mean values of test/control will have 95% confidence intervals constructed for each treatment regimen versus the Breg Cooling Control Group. For a treatment regimen to be considered clinically acceptable, it must be no more than 30% worse than the Breg Cooling Control Group and the lower limit of the 95% confidence interval for the treatment regimen must be greater than 0.7. This analysis will be performed on the ITT population.

13-Jun-2019

# Confidential

	For analysis, satisfaction scores (SS and IS) and 30 minute pain after CNTX-4975-05
	injection will be transformed to equivalent scales, and 30 minute pain after CNTX-4975-05 injection will be reverse-scored so that higher scores represent lower pain, in order to have the 3 components on the same scale before they are combined by summing the 3 scores for a composite score. A sensitivity analysis will be performed that creates a composite score using the original scales (with the pain scores still reverse-scored to ensure the direction of the effect remains the same), using the ITT population.
	All other continuous secondary and exploratory efficacy endpoints will be summarized using descriptive statistics by subject type, experimental injection procedure, and week/visit, as appropriate, and analyzed using a mixed-model repeated measures analysis or by analysis of covariance, as appropriate. Categorical endpoints will be compared between treatments using Pearson's chi-square or Fisher's exact test, as appropriate.
	Safety analyses will be conducted using data from the safety population.
SAMPLE SIZE DETERMINATION	Approximately 850 subjects will receive CNTX-4975-05 in an open-label manner. This sample size was chosen based on the need to fulfill safety requirements for regulatory review.
STUDY AND TREATMENT DURATION	The overall study duration is expected to be 13 months, with 10 months of active enrollment and about 3 months for screening and treatment follow-up. The sequence and maximum duration of the study periods will be as follows:
	Screening Period up to 15 days.
	Treatment Period (open-label): 1 day per knee treated, maximum 2 days
	Post-treatment period: 8 weeks from the first CNTX-4975-05 IA injection
	The maximum CNTX-4975-05 treatment for each subject is 2 days.
	The maximum study duration for each subject is approximately 10 weeks.

AD-MW-08.04 15-Apr-2016 Page 14 of 89

Amendment 2 Version: 3.0

# 2 SCHEDULE OF EVENTS

**Table 2-1: Schedule of Events** 

	Screening Visit	Treatment #1 (single knee)*	Phone F/U	Treatment #2 (Bilateral knees only)*	Phone F/U (Bilateral knees only)	Efficacy Safety	Efficacy Safety/ Early Termination Visit
Clinic Visit (V) or Telephone Visit (TV)	V1	V2	TV3ª	V4 b	TV5 a,b	V6	V7
Study Day/Week	Day -14 to Day 1°	Day 1	Day 3 ±1d	Day 7 (Week 2) (-2/+5 d)	V4 +3d ±1d	Week 4 ±5d	Week 8 ± 7d d
Informed consent	X						
Confirmation of OA of the knee (K-L grade 1-4) based on radiographs e	X						
Confirmation of OA of the knee based on American College of Rheumatology diagnostic criteria	X						
Inclusion/exclusion criteria	X						
Height and weight (including body mass index)	X						
History of cancer	X						
Knee pain with walking (last 24 hours; NPRS of 0-10)	X	X h	X	X h	X	X	X
Demographics, medical history, OA medications & treatment history f	X						
Hospital Anxiety and Depression Scale (HADS)	X						
Fibromyalgia Symptom Scale Score (FSS)	X						
Knee circumference	X						
Physical examination g	X	X h		X h			X
12-Lead electrocardiogram	X	X h					X
Clinical laboratory testing i	X			Xi			X
Urine drug screen j	X	X h				X	X
Urine pregnancy test k	X	$X^h$		X h		X	X
Vital signs	X	X l		X 		X	X

13-Jun-2019 Amendment 2 Version: 3.0

AD-MW-08.04 15-Apr-2016 Page 15 of 89

	Screening Visit	Treatment #1 (single knee)*	Phone F/U	Treatment #2 (Bilateral knees only)*	Phone F/U (Bilateral knees only)	Efficacy Safety	Efficacy Safety/ Early Termination Visit
Clinic Visit (V) or Telephone Visit (TV)	V1	V2	TV3 a	V4 b	TV5 a,b	V6	V7
Study Day/Week	Day -14 to Day 1°	Day 1	Day 3 ±1d	Day 7 (Week 2) (-2/+5 d)	V4 +3d ±1d	Week 4 ±5d	Week 8 ± 7d d
Issue/review/collect paper diary	X	X h		X h		X	X
Sensory testing		Xh		Xh			X
CNTX-4975-05 injection (dosing)  (30-minute post-injection observation required)		X		X			
Injection site assessment (erythema, edema) n		X		X		X	
Subject assessment of procedure pain (scale of 0-4) °		X	X	X	X		
Knee Injury and Osteoarthritis Outcome Score (KOOS)		Xw				X	X
Subject satisfaction with treatment procedure p		X	X	X	X	X	X
Subject satisfaction with PJR/TJR (as applicable) p						X	X
Retreatment question q							X
Investigator satisfaction questionnaire r		X		X			X
Joint replacement questionnaires		X					X
Adverse events t		X	X	X	X	X	X
Review use of background, analgesic, rescue, and other concomitant medications and therapies u,v Abbrevietions: A E-adverse quent: d=deve of RE-alectronic	X	X	X	X	X	X	X

Abbreviations: AE=adverse event; d=day; eCRF=electronic case report form; ET=early termination; f/u=follow-up; IA=intra-articular; K-L=Kellgren-Lawrence; NPRS=numeric pain rating scale; NSAID=non-steroidal anti-inflammatory drug; OA=osteoarthritis; PI=principal investigator; PJR=partial joint replacement; TJR=total joint replacement; TV=telephone visit; V=clinic visit

- a. On Day 3 post-injection (±1 day), study staff will call subjects to assess OA pain, AEs, subject assessment of procedure pain and satisfaction, knee pain with walking, and the use of rescue medication (for bilateral knee injections, calls will occur 3 days after each injection).
- b. Only subjects receiving bilateral knee injections will have Visit 4 and Telephone Visit 5.
- c. If subjects are unable to complete the screening assessments due to technical issues, the site is permitted a 3 business day window to complete the assessments (Screening Period of up to 17 days instead of 14 days).

13-Jun-2019 Amendment 2 Version: 3.0

AD-MW-08.04 15-Apr-2016 Page 16 of 89

\* Sites where crash carts and ACLS-certified personnel are not immediately available will have a window of +/- 14 business days to schedule injections. Once a crash cart and ACLS-certified personnel are available at these sites then all standard windows apply.

- d. If a subject is discontinuing the study before Week 8, the assessments listed for the Week 8/ET Visit should be completed.
- e. A pre-screening radiograph of both knees must show evidence of chronic OA with a K-L grade of 1 to 4 in the index knee as determined by the site PI or radiologist. If the subject has radiographs from Centrexion study CNTX-4975i-OA-301 or CNTX-4975i-OA-304, those radiographs and K-L grading should be used for this study.
- f. Medical history and demographics, as outlined in the eCRFs. OA medications should note all therapies, including doses and regimen when known, and all should note if the medications were over the counter or prescriptions. Treatments to be recorded include non-invasive treatments (e.g., physical therapy) and previous invasive treatments (e.g., arthrotomy, arthroscopy with procedure, if known).
- g. A complete physical examination (excluding a genitourinary examination) will be performed by the investigator at the Screening Visit and at the final clinic visit (Week 8/ET). A partial physical examination will be performed by the investigator before each injection). The physical examinations will also evaluate the soft tissue of the index knee for periarticular painful sites, which will be entered onto the case report form.
- h. To be performed before injection of CNTX-4975-05.
- i. Clinical laboratory tests will include chemistry, hematology, and urinalysis. Additional tests, including fibrinogen and prothrombin time/partial thromboplastin time, will be done at Screening only. Hemoglobin A1c will be done at the Screening and Week 8/ET Visits. Subjects are to fast prior to the laboratory sample collections performed at the Screening Visit. If the subject is receiving a second knee injection (in the contralateral knee), labs are not required to be repeated if the injection is within 30 days of the screening lab draw (at the investigator's discretion).
- j. Urine drug screen must be confirmed as negative for drugs of abuse prior to treatment. For subjects being treated bilaterally, a Urine Drug Screen is not required prior to the second injection.
- k. Subjects will be tested for pregnancy if they are women of childbearing potential. A serum pregnancy test will be performed if the urine pregnancy test is positive. Subjects with positive urine pregnancy test results will not be enrolled or will be discontinued from study participation. These subjects will be followed until the pregnancy is completed, and the health of the infant is known.
- 1. Vital signs are to be performed standing and sitting within approximately 5 minutes before the injection of IP, and sitting-only vital signs within approximately 5, 15, and 30 minutes minutes after the injection of IP.
- m. Each site is to follow their assigned, protocol-specified treatment regimen and the protocol-specified CNTX-4975-05 administration procedures.
- n. The injection site will be examined and assessed for erythema and edema by site personnel (using a categorical 4-point scale of none, mild, moderate, or severe [0-3]) on Study Day 1 (Treatment) before injection, after the injection at 1 and 2 hours post-dose, and at the Week 4 Visit. For bilateral knee injections, injection site examinations will be performed before and after each injection. Significant bruising or other clinically significant injection site reactions will be recorded as AEs.
- o. Procedure pain will be assessed by asking subjects to rate their index knee pain (1) at rest prior to pre-medication; (2) prior to IA lidocaine (without epinephrine); (3) at rest 10 minutes (± 2 minutes) after IA lidocaine (without epinephrine); (4) at 30 minutes (± 5 minutes) after IA injection of CNTX-4975-05; and (5) at rest at the 1-hour and 2-hour time points after IA injection of CNTX-4975-05 (± 10 minutes).
- p. Immediately prior to leaving the clinic, the subject will be asked how satisfied they were with the treatment procedure at that visit, using a 7-point Likert Scale where 1=completely dissatisfied and 7=completely satisfied. Subjects with a PJR/TJR will also compare their satisfaction with PJR/TJR versus the CNTX-4975-05 treatment.
- q. Subjects will be asked whether they would undergo the study treatment again.
- r. The investigator will rate their satisfaction with each subject's study treatment (at V2 and V4 if applicable) and the treatment procedure (at V7).
- s. The investigator will judge the likelihood of the need for joint replacement surgery, based on KOOS subscales and subject satisfaction outcomes. The subject will judge the likelihood of the desire for joint replacement surgery, based on their personal response to treatment with CNTX-4975-05.
- t. Collection of AEs will begin from the time of signing the informed consent form through the Week 8/ET Visit. On Day 1, the AE assessment must be performed pre-dose. Treatment-emergent AEs will be collected from the time of the injection of CNTX-4975-05 through the Week 8/ET Visit. Potentially

13-Jun-2019 Amendment 2 Version: 3.0

AD-MW-08.04 15-Apr-2016 Page 17 of 89

- related AEs that are ongoing at the Week 8/ET Visit will be followed until they are stable, resolved, no longer clinically significant (in the opinion of the investigator), or until 4 weeks after the study is completed.
- u. Subjects may come into the study with a single analgesic of their choice for their OA knee pain (prescription or OTC). The current pain medication must be identified as that taken only for OA knee pain, not for another pain indication. The subjects will complete a daily paper diary of their background knee analgesic medications during the screening period and throughout the trial.
- v. Subjects may take rescue medication for pain of the index knee as needed. Subjects should not take rescue medication within 24 hours prior to a clinic visit. Data on the type of rescue medication, and the daily dose of rescue medication, will be collected and will be recorded each day in their paper diary. Additional rescue medication details will be collected at study visits and follow-up telephone calls and recorded in the source documents and eCRF.
- w. For subjects being treated bilaterally, KOOS will be assessed on both knees prior to the first injection but is not required to be completed prior to the second injection.

13-Jun-2019 Amendment 2 Version: 3.0

AD-MW-08.04 15-Apr-2016 Page 18 of 89

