- 12. Corticosteroid injection into the index or contralateral knee within 90 days of Screening.
- 13. Received IA viscosupplementation (e.g., Synvisc®, Hyalgan®) within 90 days of Screening.
- 14. History of allergic reaction to the planned local anesthesia/analgesic regimens, ethylenediaminetetraacetic acid, Kolliphor HS 15, butylated hydroxytoluene, or capsaicin.
- 15. Presence of any medical condition or unstable health status that, in the judgment of the investigator, might adversely impact the safety of the subject, or the conduct of the study, or negatively affect the resulting data, including chronic conditions that are likely to alter the rate of healing or are likely to result in safety complications unrelated to the study

medication, or significantly compromise key organ systems. For any question regarding eligibility, it is strongly recommended that the investigator discuss the subject with the medical monitor.

- 16. Is pregnant or is breast feeding.
- 17. Has a malignancy, a history of malignancy, or has received treatment for malignancy at any time, with exception of resected and cured basal cell carcinoma and squamous cell carcinoma of the skin.
- 18. Regular use of anticoagulant blood thinners (except low-dose aspirin, Dabigatran 150 mg once daily [qd], Enoxaparin 40 mg qd, Rivaroxaban 10 mg qd, or Apixaban 2.5 mg twice daily [bid], or clopidogrel 75 mg qd, which are allowed).
- 19. Active cutaneous disease at the anticipated site of CNTX-4975-05 injection that would prevent the safe administration of CNTX-4975-05.
- 20. Ulcer or open wound anywhere on the index knee.
- 21. Specific laboratory abnormalities:
  - Hemoglobin <11.0 g/dL

  - White blood cells  $< 2.5 \times 10^9/L$
  - Neutrophils  $< 1.5 \times 10^9/L$
  - Platelets  $<100 \times 10^9/L$
  - Aspartate transaminase or alanine transaminase >2 × upper limit of normal
  - Creatinine >1.6 mg/dL
  - Glucose (fasting) >250 mg/dL
  - Hemoglobin A1c (HgbA1c) >9.0%
- 22. Clinically significant abnormal laboratory result at the Screening Visit (in the opinion of the investigator), or significant organ disease that would put the subject at undue risk or affect the ability of the subject to participate in the trial. For any question regarding eligibility, it is strongly recommended that the investigator discusses the subject with the medical monitor.

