#### 10.1 Study Visits

### 10.1.1 Screening Visit, Day -14 to Day 1, Visit 1

The subject must be screened within 14 days before enrollment into the study. The following procedures will be performed at screening.

- Written informed consent
- Confirmation of knee OA K-L grade (1 to 4) of the knee, based on radiographs
- Confirmation of diagnosis of knee OA, based on ACR diagnostic criteria
- Inclusion/exclusion criteria
- Height and weight (BMI)
- History of cancer
- Knee pain with walking (during last 24 hours, assessed in the clinic using NPRS of 0-10)
- Demographics
- Medical history, including current OA medications (prescription and non-prescription medications) and treatment history (including noninvasive or previous invasive treatments)
- HADS
- FSS
- Knee circumference
- Complete physical examination
- ECG
- Clinical laboratory testing (fasting)
- Urine drug screen
- Urine pregnancy test
- Vital signs
- Issue paper diary to the subject with instructions on use and recording of background analgesic and rescue medication for index knee (or bilateral knee for subjects being treated for both knees)

### 10.1.2 Treatment, Day 1, Visit 2

As 2 cases of severe allergic reactions have occurred in the entire CNTX-4975 program, a crash cart and personnel certified in advanced cardiac life support (ACLS) should be immediately available. See section 11.2.1 for details.

The following procedures will be performed on Day 1.

- Knee pain with walking (during last 24 hours, assessed in the clinic using NPRS of 0-10)
- Partial physical examination
- ECG
- Urine drug screen
- Urine pregnancy test
- Vital signs (before and after injection of CNTX-4975-05). All subjects must be monitored for at least 30 minutes (or longer, as required by the protocol) after study drug injection to ensure that they do not have a hypersensitivity reaction/anaphylaxis. Vital signs (VS) are to be done standing and sitting within approximately 5 minutes before the injection of IP, and sitting-only vital signs within approximately 5, 15, and 30 minutes after the injection of IP.
- Injection site assessment (erythema, edema) before injection and 1 and 2 hours after the injection
- Review paper diary
- Sensory testing
- Subject assessment of procedure pain (using 0-4 scale)
  - o at rest prior to pre-medication;
  - o prior to IA lidocaine (without epinephrine);
  - o at rest 10 minutes (±2 minutes) after IA lidocaine (without epinephrine);

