### 10.1.7 Week 8, Visit 7 (or Early Termination)

- Knee pain with walking (during last 24 hours, assessed in the clinic using NPRS of 0-10)
- Complete physical examination
- ECG
- Clinical laboratory testing
- Urine drug screen

- Urine pregnancy test
- Vital signs
- Sensory testing
- Review and collect paper diary
- KOOS
- SS with study treatment
- SS with PJR/TJR (if applicable)
- Subject retreatment question
- IS questionnaire
- Joint replacement questionnaire
- AEs
- Review use of background, analgesic, rescue, and other concomitant medications and therapies

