### 10.3.3.1 Laboratory Safety Assessments

### 10.3.3.1.1 Laboratory Tests to be Performed

Samples for the following laboratory tests will be collected at the time points specified in the schedule of events (Section 2).

Hematology hemoglobin, hematocrit, red blood cell count, red blood cell indices,

mean corpuscular hemoglobin, mean corpuscular hemoglobin concentration, platelet count (or estimate), white blood cell count

including differential

Serum Chemistry albumin, total bilirubin, total protein, calcium, alkaline phosphatase,

alanine aminotransferase, aspartate aminotransferase, blood urea nitrogen, creatinine, glucose, sodium, potassium, chloride,

bicarbonate, lactate dehydrogenase, uric acid

Coagulation Panel prothrombin time, partial thromboplastin time, fibrinogen

Urinalysis pH, specific gravity, occult blood, leukocyte esterase, glucose, protein,

ketones

Urine Pregnancy Test Only for women of childbearing potential. A serum pregnancy test will

be performed if the urine pregnancy test is positive.

Urine Drug Screen amphetamines, barbiturates, benzodiazepines, cocaine, opiates,

phencyclidine, and tetrahydrocannabinol

Other HgbA1c

Knee Radiographs Radiographs of both knees using standard standing films or using the

fixed flexion method. Scoring will use the Kellgren-Lawrence Grading

Scale.

Blood and urine samples for hematology, serum chemistry, and urinalysis will be sent to a central laboratory for analyses. Urine drug screens and urine pregnancy tests may be conducted at the study sites.

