#### 13.4.4.2 Clinical Laboratory Evaluations

Descriptive summaries (mean, SD, median, minimum, and maximum) of actual (absolute) values and changes from Baseline values will be presented for clinical laboratory values at each time point.

The number of subjects with clinical laboratory values categorized as below, within, or above normal ranges, will be tabulated showing change from Baseline (shift tables) for each clinical laboratory analyte by study visit. Pre- and post-treatment values will also be presented with analysis summary of mean changes from Baseline.

Laboratory values that are outside the normal range will also be flagged in the data listings, along with corresponding normal ranges. Any out-of-range values that are identified by the investigator as being clinically significant will be reported as AEs.

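### Fasting is required only for the Screening laboratory sample, which acts as Baseline, so the Week 8 glucose change and shift tables may be biased upward by an amount that cannot be estimated from the plan

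*Combined protocol and SAP*

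**What the plan says.** **Sampling conditions.** Footnote i to Table 2-1 states: "Subjects are to fast prior to the laboratory sample collections performed at the Screening Visit". The visit list for Screening (Section 10.1.1) agrees: "Clinical laboratory testing (fasting" is the entry, with fasting as the bracketed condition. The list for Week 8/Early Termination (Section 10.1.7) has only "Clinical laboratory testing", with no condition. The list for Visit 4, the second injection in bilaterally treated subjects (Section 10.1.4), also gives no fasting condition.

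**What is measured.** Glucose belongs to the repeated serum chemistry panel (Section 10.3.3.1.1: "nitrogen, creatinine, glucose, sodium, potassium, chloride"). Fasting at Screening serves eligibility, because exclusion criterion 21 includes "Glucose (fasting) >250 mg/dL" (Section 8.2.2).

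**What is tabulated.** Under Section 13.4.4.2, "changes from Baseline values will be presented for clinical laboratory values at each time point". In addition, counts below, within and above the normal range "will be tabulated showing change from Baseline (shift tables) for each clinical laboratory analyte by study visit". Glucose gets no separate handling, and no fasting flag is mentioned.

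**Who is treated.** All enrolled subjects receive CNTX-4975-05 (Section 9.5). The five regimens differ only in cooling, needle and lidocaine concentration.

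**The concern.** A change from Baseline is interpretable when both samples are taken under the same conditions. Here the first glucose value is fasting by instruction, and the condition of the later one is left open. If some subjects have eaten before the Week 8 draw, the mean change will include a fed-minus-fasted difference, and some subjects will move from within to above the normal range for that reason alone. The same bias could also offset a true fall.

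A placebo group would show the same artefact and allow it to be subtracted. This trial has none. The five regimens would all carry the artefact, so comparing them neither reveals nor removes it. Section 13.2 says that the sample size was chosen to meet safety requirements for regulatory review, so the safety tables are a main product of the study and should be readable on their own.

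**Working it through.** The plan states no glucose mean, standard deviation or expected change, so there is no figure to reproduce. The check has three steps.

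**Step 1: which sample is Baseline.** Table 2-1 marks clinical laboratory testing at Screening, Visit 4 and Week 8/Early Termination, and not at Visit 2 (Day 1). Laboratory Baseline is not defined, but Screening is the only scheduled draw before the first dose. The reference value for glucose is therefore the fasting one.

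**Step 2: which later visit matters.** Footnote i lets the investigator skip the Visit 4 labs if the second injection falls within 30 days of the Screening draw. With no Day 0,

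gap in days = lead from Screening draw to Day 1 + Visit 4 day − 1.

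The Visit 4 window is Day 7 (−2/+5 days), that is, Day 5 to Day 12.

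| Screening lead | Visit 4 day | Gap (days) |
|---|---|---|
| 14 | 7 | 14 + 7 − 1 = 20 |
| 14 | 12 | 14 + 12 − 1 = 25 |
| 17 (footnote c) | 12 | 17 + 12 − 1 = 28 |
| 19 (3 business days spanning a weekend) | 12 | 19 + 12 − 1 = 30 |

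Under every standard window the gap is at most 30 days, so the waiver is available. Only the temporary ±14 business day allowance, for sites without a crash cart and certified staff, exceeds it. Taking 14 business days as 18 to 20 calendar days, the gap after a 14-day lead is between 20 + 18 = 38 and 25 + 20 = 45 days. Visit 4 applies to bilateral subjects only, so it should contribute few samples. Week 8/Early Termination is scheduled for everyone and carries the point.

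**Step 3: size, by illustration only.** Let f be the share of subjects not fasting at Week 8, and d the mean fed-minus-fasted glucose difference. With no drug effect,

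spurious mean change = f × d.

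Neither input is in the documents. The values below are assumptions, in mg/dL.

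| f | d = 5 | d = 15 | d = 30 |
|---|---|---|---|
| 0 | 0 | 0 | 0 |
| 0.25 | 1.25 | 3.75 | 7.5 |
| 0.5 | 2.5 | 7.5 | 15 |
| 1 | 5 | 15 | 30 |

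To judge whether such a shift would show, take the planned 850 subjects, an upper limit on the number with a Week 8 value, and assume a standard deviation of change of 15 to 40 mg/dL. The 95% half-width of the mean change is 1.96 × SD / √850, which is 1.0 mg/dL at SD 15 and 2.7 mg/dL at SD 40. Seven of the nine non-zero entries exceed even the wider of these. Most of the assumed range would therefore be visible in the overall mean.

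If fasting were required at Week 8 and followed, f = 0 and the artefact is zero for any d.

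**The case against.** The best case for the plan has four parts.

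- **The documents are silent about later draws.** A reader might infer that the Week 8 samples are non-fasting and that a glucose rise is built in. No section says so. Fasting is unspecified, and if subjects happen to fast there is no artefact. This stands and sets the limit of the point: bias is likely in direction and unknown in size. Silence still leaves the table unreadable, because no fasting status is recorded from which to tell comparable values from others.
- **Fasting at Screening has its own purpose.** It supports the fasting-glucose exclusion, so the instruction is coherent and contradicts nothing. That is correct. The difficulty comes from reusing the same sample as Baseline.
- **HgbA1c is drawn at Screening and Week 8/Early Termination** (footnote i), so glycaemia is not unmonitored. This stands as a partial cross-check. It does not correct the glucose tables, and 8 weeks is short for HgbA1c.
- **The tables are descriptive.** Section 13.4.4 plans no formal inference on safety variables unless otherwise noted, and Section 13.4 leaves details to a later statistical analysis plan. Both are true and keep the severity low.

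A reader might also infer that fed samples would inflate adverse event counts. The documents do not support that: Section 10.3.3.1.3 says that an out-of-range value need not be clinically relevant and requires the investigator's assessment. Any effect on adverse events is speculation.

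**Conclusion.** The point holds in a limited form. Followed as written, the plan compares a fasting Baseline glucose with a Week 8/Early Termination glucose taken under uncontrolled conditions. The change and shift tables may therefore be biased upward, and with no untreated group they cannot separate this from a drug effect.

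The size cannot be derived from the documents. The range of 0 to 30 mg/dL above rests entirely on assumed values of f and d, and its top end needs every subject to be non-fasting. It would go too far to call the whole Week 8 change spurious, or to put weight on Visit 4.

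The conclusion rests on two assumptions: that the Screening sample is used as laboratory Baseline, which the schedule implies but does not state, and that at least some subjects will have eaten before the Week 8 draw. The effect is confined to glucose, and to any other food-sensitive analyte, in descriptive safety tables. No efficacy endpoint is affected. This is a cheap improvement of low severity.

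**What to change.** Do one of the following.

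1. **Match the condition.** In footnote i and Section 10.1.7, apply the Screening fasting instruction to the Week 8/Early Termination draw as well. The cost is a fasting instruction before one existing visit.
2. **Record the condition.** Capture fasting status at each post-Screening draw, including Visit 4 when labs are repeated. Present the glucose change and shift tables by fasting status, with fasting-to-fasting comparisons as the main display. The cost is one eCRF field. This option also covers early termination visits held at short notice, where a fast may not be practical.

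Under either option, state in the analysis plan that Screening is the laboratory Baseline, and read the glucose tables alongside HgbA1c. Removing glucose from the tables and relying on HgbA1c alone is not recommended, because it gives up a planned safety summary.
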